### 15.2.3 Secondary Endpoint

To assess the incidence of major or minor bleeding not related to CABG. The PLATO trial observed a 1-year rate of major or minor bleeding of 14.6% in subjects receiving clopidogrel, and the genetic sub-study observed no significant decrease in major bleeding in those with loss-of-function alleles. Thus, assuming a 14.6% rate of major or minor bleeding at 12 months in reduced function subjects receiving clopidogrel, 1,694 subjects will provide 80% power if the bleeding rate in the ticagrelor group is at least 19.7%.

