### ***Ticagrelor***

Common adverse events include major and minor bleeding (8.7%), headache (6.5%), raised serum creatinine (7.4%), cough (4.9%), dyspnea (13.8%), atrial fibrillation (4.2%), and syncope (1.7%).

Ticagrelor may cause significant, sometimes fatal, bleeding. Hence patients with active pathological bleeding or history of intracranial hemorrhage, bleeding diathesis, and on chronic anticoagulation such as warfarin will be excluded.

Maintenance doses of aspirin above 100 mg reduce the effectiveness of ticagrelor; thus patients unable to take aspirin at 100 mg or less will be excluded.

In a randomized, double-blind study of patients with acute coronary syndrome, major bleeding events (not related to CABG) were reported in 4.5% of patients who received ticagrelor (n=9235) compared with 3.8% of patients who received clopidogrel (n=9186). Both were co-administered with aspirin and other standard therapy for 6 to 12 months. The bleeding episodes were fatal or life-threatening in 2.1% of ticagrelor-treated patients compared with 1.9% of clopidogrel-treated patients. Fatal events were reported in 0.2% of patients in each group. Fatal or life-threatening intracranial bleeding was reported in 0.3% and 0.2% of ticagrelor- and clopidogrel-treated patients, respectively. In a randomized, double-blind study of patients with acute coronary syndrome who underwent CABG surgery, major bleeding events were reported in 85.8% of patients who received ticagrelor (n=770) compared with 86.9% of patients who received clopidogrel (n=814). Both were co-administered with aspirin and other standard therapy for 6 to 12 months. The bleeding episodes were fatal/life-threatening in 48.1% of ticagrelor-treated

patients compared with 47.9% of clopidogrel-treated patients. Fatal bleeding events were reported in 0.9% and 1.1%, respectively, of patients.

If possible, minor bleeding should be managed without discontinuing ticagrelor therapy since therapy discontinuation increases the risk of myocardial infarction, stent thrombosis, and death. Although discontinuation increases the risk of subsequent adverse cardiovascular events, ticagrelor should be stopped 5 days prior to surgery, when possible. Hence if a surgical procedure is planned including CABG, surgery patients will be excluded since they will be unable to complete the 12-month duration of anti-platelet therapy.

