In the Platelet inhibition and patient Outcomes (PLATO) trial, patients randomized to ticagrelor prior to surgical intervention for acute coronary syndrome had significantly fewer cardiovascular deaths, MI, or stroke compared with patients on clopidogrel. This analysis of PLATO, a multicenter, randomized, double-blind, double-dummy controlled trial of ticagrelor or clopidogrel in patients aged 53 to 69 years old presenting with acute coronary syndrome, compares the composite event rates in patients undergoing invasive management (coronary angiography, percutaneous coronary intervention (PCI), coronary artery bypass graft). Ticagrelor patients ( $n=6,732$ ) received a 180 milligram (mg) loading dose then 90 mg twice daily (plus placebo clopidogrel); clopidogrel patients ( $n=6,676$ ) received a 300 mg loading dose then 75 mg once daily (plus placebo ticagrelor) for 6 to 12 months. PCI patients were eligible for an additional 300 mg clopidogrel loading dose (or placebo) at investigators' discretion (event rates did not vary significantly when stratified by clopidogrel loading dose). All patients received aspirin 75 to 100 mg per day. At 12 months post-intervention, cardiovascular death, MI or stroke (primary composite endpoint) occurred in 569 (9%) ticagrelor patients compared with 665 (10.7%) clopidogrel patients [hazard ratio, 0.84; 95% confidence interval (CI), 0.75-0.94;  $p=0.0025$ ]. Incidences of cardiovascular death (5.3% vs 6.6%;  $p=0.0023$ ) and MI (3.4% vs 4.3%;  $p=0.025$ ) were significantly lower in the ticagrelor group compared with the clopidogrel group, although the incidences of stroke were not significantly different between the 2 groups. Total major bleeding [per Thrombolysis in Myocardial Infarction (TIMI) definition] occurred in 689 ticagrelor patients (11.5%) and 691 clopidogrel patients (11.6%) (95% CI 0.89 to 1.10;  $p=0.8803$ ), and severe bleeding (per Global Use of Strategies to Open Occluded Coronary Arteries definition) occurred in 185 (2.9%) of ticagrelor patients compared with 198 (3.2%) of clopidogrel patients (95% CI 0.74 to 1.12;  $p=0.3785$ ). Dyspnea occurred more frequently in ticagrelor patients compared with clopidogrel patients (13.9% versus 8%,  $p$  less than 0.0001) and was cause for discontinuing therapy in 0.8% of the ticagrelor group.

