## 15.2 Sample Size and Power Considerations

### 15.2.1 Primary Endpoint

Sample size and power calculations for the study are based on the following assumptions:

- 2-sided log-rank test
- $\alpha = .05$
- Randomization ratio of 1:1

Data from the Mayo Rochester PCI registry demonstrate a 1 year rate of death, MI, or stroke of about 7.5% in PCIs from 2008-2009. Furthermore, the PLATO trial suggests we can expect stent thrombosis or severe, recurrent ischemia in about an additional 3%, resulting in a baseline rate of 10.5%. The rate is expected to be higher in \*2 or \*3 allele carriers who are discharged on clopidogrel, thus we assume a baseline rate of 12% for primary endpoint in the control arm.

Two studies suggest that the expected rate of 12% in Korean patients treated with clopidogrel after PCI for ACS. Kim et al. observed a 10.1% event rate for death, myocardial infarction, or stroke at 12 months in 306 patients with at least one *CYP2C19*\*2 or \*3 allele treated with PCI for acute myocardial infarction. As noted above, the PLATO trial suggests that stent thrombosis and severe recurrent ischemia may add 3% to this rate, which would result in a baseline rate over 12%. Oh et al. observed a 10.7% event rate for cardiac death, myocardial infarction and repeat revascularization at 12 months in 1011 patients treated with a drug-eluting stent (22% AMI, 78% stable) and carrying at least one *CYP2C19*\*2 allele. Assuming the event rate is higher in the

AMI subgroup and that the addition of stent thrombosis to the endpoint would increase the event rate, this study also suggests that a 12% event rate in the control group of Koreans may be expected.

Given that the vast majority of patients at the Mayo sites are of European heritage, we expect a reduced function allele prevalence of about 30% in those patients. The Canadian hospitals have a more diverse ethnic mix of patients, and we expect their prevalence to be anywhere from 30-50%. Thus, our sample size calculations assume an overall prevalence of reduced function allele carriers of 30% among patients recruited at those sites. We also assume the prevalence to be 50% in patients enrolled from South Korea and expect to enroll 1,015 subjects from there. Furthermore, we assume no more than 5% of patients will be lost to follow-up or drop out.

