## 15.6 Specification of the Secondary Analyses

For secondary analyses involving 1-year endpoints (e.g. MACE, bleeding), Cox proportional hazards models with appropriate covariates will be used to compare the 1-year rate of secondary endpoints according to intention-to-treat classification. A p-value less than 0.05 will be considered statistically significant. Additionally, unadjusted treatment effects will also be estimated and tested as a secondary analysis. Confidence intervals for binomial measures will be computed using the Wilson CI method for 95% coverage probability. Mechanisms of stent failure for subjects with coronary stent thrombosis and with reduced function *CYP2C19* allele will be compared between ticagrelor and clopidogrel using Pearson's chi-squared test.

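### The bleeding power statement pairs a non-CABG endpoint with a 14.6% clopidogrel rate that appears to include CABG bleeding; the detectable effect should be restated

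*Combined protocol and SAP*

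**What the plan says.** Section 15.2.3 opens with the endpoint: "To assess the incidence of major or minor bleeding not related to CABG". The control rate follows: "The PLATO trial observed a 1-year rate of major or minor bleeding of 14.6% in subjects receiving clopidogrel", with no statement of whether CABG bleeding is counted. The power claim is "1,694 subjects will provide 80% power if the bleeding rate in the ticagrelor group is at least 19.7" per cent.

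The CABG exclusion appears only there. Section 2.2 (secondary aim), Section 12.2 (secondary outcome) and the bleeding definitions in Section 12.3 refer to major or minor bleeding without it.

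Section 15.2.3 names no test. Section 15.2.1 lists a "2-sided log-rank test" with 1:1 allocation for the primary endpoint. For secondary analyses, Section 15.6 plans Cox models and says: "A p-value less than 0.05 will be considered statistically significant".

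**The concern.** A power statement holds only if its control rate belongs to the endpoint being tested. Elsewhere the protocol gives non-CABG major bleeding of only 3.8% on clopidogrel, and CABG patients contribute a large number of further major bleeds. A rate of 14.6% therefore looks like an all-bleeding rate applied to a non-CABG endpoint.

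Bleeding is the only secondary outcome, and it is the safety counterpart to the primary efficacy question. If the true control rate is well below 14.6%, the trial can detect only a larger relative increase on ticagrelor than Section 15.2.3 implies. A reader who takes the 80% at face value would give too much weight to a non-significant bleeding comparison.

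**Working it through.** **1. The stated figure reproduces.** Inputs: 847 per arm (1,694 / 2), p1 = 0.146, p2 = 0.197, two-sided alpha 0.05.

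- Two proportions: power = Φ{[|p2 − p1|√n − 1.96√(2p̄q̄)] / √(p1q1 + p2q2)}, with p̄ = 0.1715. This is Φ{[1.484 − 1.045] / 0.532} = Φ(0.826) = 79.6%.
- Log-rank (Schoenfeld): HR = ln(1 − 0.197) / ln(1 − 0.146) = 1.390. Expected events = 847 × (0.146 + 0.197) = 290.5. Power = Φ(√290.5 / 2 × ln 1.390 − 1.96) = Φ(0.847) = 80.2%.

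The implied rate ratio is 0.197 / 0.146 = 1.35 and the implied difference is 5.1 points.

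**2. Does 14.6% fit a non-CABG endpoint?**

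- Section 7.6.2 (Ticagrelor) gives non-CABG major bleeding of 3.8% on clopidogrel (n = 9,186) and 4.5% on ticagrelor. Among CABG patients on clopidogrel, 86.9% of 814 had major bleeding: 0.869 × 814 = 707, and 707 / 9,186 = 7.7%.
- 3.8% + 7.7% = 11.5%. Section 7.6.2 (Clopidogrel) reports 11.6% total major bleeding. The remaining 14.6 − 11.5 = 3.1 points are a plausible size for minor bleeding.
- Appendix A (Ticagrelor Side Effects) lists 8.7% major plus minor bleeding beside the same 4.5% that Section 7.6.2 labels non-CABG. Minor bleeding on ticagrelor is then about 8.7 − 4.5 = 4.2 points.
- If 14.6% were non-CABG, minor bleeding on clopidogrel would have to add 14.6 − 3.8 = 10.8 points, and clopidogrel would bleed 14.6 / 8.7 = 1.7 times as often as ticagrelor. Section 3 says that ticagrelor increased non-CABG bleeding.

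**3. A range for the matching rate (assumption).** The documents do not give this rate. Pointers are 14.6 − 7.7 = 6.9%; 8.7 / (4.5 / 3.8) = 7.35%; 8.7% itself as a ceiling if ticagrelor bleeds more; and 3.7 + 5.1 = 8.8%, the sum of the upper limits for clopidogrel in Appendix A. I use 7% to 8.8%.

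**4. Power at N = 1,694, two-sided 0.05.**

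| Clopidogrel rate | Power, rate ratio 1.35 (two proportions) | Power, HR 1.39 (log-rank) | Ticagrelor rate for 80% power (two proportions) | Power, fixed 5.1-point difference (two proportions) |
|---|---|---|---|---|
| 14.6% (plan) | 79.6% | 80.2% | 19.7% (ratio 1.35) | 79.6% |
| 7.0% | 44.9% | 49.7% | 10.9% (1.55) | 94.7% |
| 7.5% | 47.7% | 52.4% | 11.5% (1.53) | 93.8% |
| 8.7% | 54.2% | 58.5% | 12.9% (1.49) | 91.4% |
| 8.8% | 54.7% | 59.0% | 13.0% (1.48) | 91.2% |

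Example, log-rank at 7.0%: ticagrelor rate = 1 − 0.93^1.390 = 9.6%; events = 847 × (0.070 + 0.096) = 140.6; power = Φ(√140.6 / 2 × 0.329 − 1.96) = Φ(−0.007) = 49.7%.

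**5. Sensitivity to N.** Interpolating Table 4 to 5,270 enrolled gives 1,784 + (115 / 930) × 302 = 1,821 evaluable carriers. The log-rank test statistic scales by √(1,821 / 1,694) = 1.037. Power becomes Φ(1.953 × 1.037 − 1.96) = 53% at 7.0% and Φ(2.187 × 1.037 − 1.96) = 62% at 8.8%.

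**The case against.** The strongest reply has four parts.

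**The source of 14.6% is inferred.** No passage says that it includes CABG bleeding. The 11.6% comes from the invasively managed cohort (6,676 on clopidogrel) and is labelled as a TIMI-definition rate. The 3.8% has a different denominator and no stated definition. The 707 / 9,186 is a crude proportion set against a 1-year rate, and it treats every major bleed in a CABG patient as CABG-related. This stands: a reader might infer that CABG content is proven, and it is not. The match with 11.6% is supporting evidence only. The comparison with ticagrelor's 8.7% does not depend on it.

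**No replacement rate is sourced.** A reader might take 6.9%, or any point in the range, as the correct rate. The documents do not support that. The Appendix A figure for clopidogrel is for non-major rather than minor bleeding, and none of these figures is tied to the haemoglobin thresholds in Section 12.3. The true rate could lie outside 7% to 8.8%.

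**The loss depends on the scale.** Section 15.2.3 states two rates, not a ratio, and absolute excess is a reasonable scale for harm. At the same 5.1 points, power rises to 91-95%. This stands, so a flat claim that the trial is underpowered for bleeding would be wrong. But 5.1 points above 7% is 12.1%, a ratio of 1.73, whereas the non-CABG major bleeding ratio in Section 7.6.2 is 4.5 / 3.8 = 1.18.

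**Nothing is decided on this statement.** The trial is not sized on bleeding, no stopping rule uses the figure, Section 15.6 already plans effect estimates and intervals, and no passage says that non-significance will be read as safety. All true. This limits the seriousness but does not make the sentence correct.

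The stray item might also be the CABG phrase rather than the rate. Dropping the phrase would not by itself validate 14.6%, because Section 7.6.2 says that patients with planned CABG will be excluded, so this trial should see fewer CABG bleeds than the source trial.

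**Conclusion.** The point holds as a mismatch between endpoint and input, not as a calculation error. A clopidogrel rate of 14.6% is implausible for non-CABG major or minor bleeding on the protocol's own figures, so the printed combination of 14.6%, 19.7% and 80% does not describe the endpoint named in the same paragraph.

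The size is conditional on an assumed control rate of 7% to 8.8%, N = 1,694, 1:1 allocation and two-sided 0.05. Power for the implied relative effect is then roughly 45% to 59% across the two methods, in place of 80%. The ratio detectable with 80% power moves from 1.35 to about 1.5, while the detectable absolute difference shrinks from 5.1 to about 3.9 to 4.2 points (10.9 − 7.0; 13.0 − 8.8). The larger number of carriers implied by Table 4 raises the log-rank figures only to about 53-62%.

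The primary analysis and the enrolment target are unaffected.

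**What to change.** 1. Decide whether CABG-related bleeding is excluded, and say so identically in Sections 2.2, 12.2, 12.3 and 15.2.3.
2. Replace 14.6% with a rate for that endpoint under the Section 12.3 definitions: either one from a named source, with its CABG handling and bleeding definition stated, or the blinded pooled rate observed so far in reduced-function subjects.
3. Restate the detectable ticagrelor rate for 80% power, naming the test and N, on both the absolute and the relative scale. For illustration only: from 7.0% it is about 10.9% (3.9 points, ratio 1.55), and from 8.8% about 13.0% (4.2 points, ratio 1.48).
4. Add that the bleeding comparison will be reported with its confidence interval, so that a non-significant result is not left to rest on the power claim.

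The cost is one recalculated sentence and a wording check across four sections. The detectable ratio will look less favourable. No change to enrolment, follow-up or the primary analysis is needed.

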### 15.3 Randomization

Subjects will be randomized on a 1:1 ratio stratified by age, sex, site, and CAD presentation, i.e. unstable angina/NSTEMI, STEMI, or stable CAD.

## 15.4 Statistical Comparisons of Baseline Factors

For continuous variables such as age, means, and standard deviations overall and within treatment group will be calculated. If the variable is moderately to severely skewed, medians and 25th and 75th percentiles will be computed. For discrete variables, frequencies and percentages will be calculated both overall and within treatment group. Standardized differences will be used as a measure of imbalance between the groups.

## 15.5 Specification of the Primary Analyses

Hypothesis 1A. The effect of genotype-guided antiplatelet therapy versus conventional care in patients with a reduced function *CYP2C19* allele will be estimated using a Cox proportional hazards regression model, with covariates including variables used for stratified randomization and other subject factors associated with MACE. The analysis will be conducted under the intention-to-treat principle, with follow-up beginning at randomization, but with genotype defined by the Taqman genotyping assay. Those whose prospectively defined genotype disagrees with their TaqMan-based genotype will nevertheless be analyzed based on the TaqMan result, which is the only result that is available in both arms. A sensitivity analysis will be done, taking into account the Spartan result. In the retrospective genotyping group, reduced function status will be determined by the TaqMan assay results at least one year after PCI. Subjects who withdraw or are lost during follow-up will be treated as censored at the date of last contact. Patients who complete follow-up at 12 months will be considered censored from that point onward. The proportional hazards assumption will be assessed visually using plots of scaled Schoenfeld residuals. A two-sided likelihood ratio test will be used to assess the significance of the partial effect of treatment; a p-value less than 0.05 will be considered statistically significant. Kaplan- Meier curves will be used to display survival free of MACE estimates over the first year of follow-up.

Hypothesis 1B. It is also important to determine the effect of genotype-guided antiplatelet therapy versus conventional care in patients with the wild type *CYP2C19* allele. In this case, both groups will be given clopidogrel, but the genotype-guided group patients and their physicians will know prospectively that they have the wild-type allele, at least based on the Spartan platform. The analysis will be done as outlined above in the LOF group, again defined by the TaqMan-based assessment of wild-type status. It is expected that the null hypothesis will prevail, but it is important to confirm that knowledge of genotype in and of itself does not have an effect on the rate of MACE events.

Finally, note that the entire allocation of type 1 error is placed on Hypothesis 1A, and the analysis of Hypothesis 1B is seen as confirmatory of the null hypothesis. If the null hypothesis in 1A is rejected, i.e. a treatment benefit is seen with ticagrelor versus clopidogrel in LOF patients (or the converse), then (and only then) a formal test of Hypothesis 1B will be conducted at the 0.05 level. The purpose of this second test is to inform the overall assessment of treatment effect in the entire randomized study population. In any case, an assessment of treatment effect in the overall randomized study population will be done for estimation and descriptive purposes only, since it will have insufficient power to detect a treatment effect. If the null hypothesis in 1B is rejected, then that result will be factored into any overall assessment of benefit of the prospective genotyping treatment strategy.

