## 15.8 Monitoring for Futility and Efficacy

Both efficacy and futility monitoring require three estimates: 1) a best current estimate of the treatment effect, as well as 2) uncertainty of the estimate (standard error and/or confidence interval), and 3) an estimate of what proportion of the study's final information is currently in hand, that is, the current value of "information time".

Information time is critical both in assessing conditional power (futility) as well as in doing interim testing using group sequential approaches. Appendix C details how to

construct a combined likelihood combining the information from the complete and the incomplete subject data, which produces the first two required estimates, using likelihood calculations, and specifically, using the profile likelihood method to get down to the one-dimensional likelihood for the treatment effect parameter.

Appendix C also details how to estimate information time (the third required measure). Once we have a current z-score (effect divided by standard error) for the treatment effect, as well as our current estimate of information time, we can then do standard calculations for conditional power (futility) and efficacy

**Futility Monitoring:** We propose that this assessment be based on our calculation of conditional power, as described in Appendix C. In addition to the conditional power calculation, we will provide the modified unconditional power calculation based on current estimates of event rates and the estimate and 95% CI of the average event rate in LOF subjects. We specifically propose that at the time of DSMB reviews, that consideration be given to stopping the trial if the ratio of conditional power to initial power falls below the proportion of remaining information time. For example, if the initial power is 85%, and the proportion of remaining information time is 40%, then the conditional power should exceed 34% ( $0.85 \times 0.4$ ). The basis for the moving target of conditional power is the “sunk cost” argument. The initial study design is assumed to equate the expected utility of a positive result with the cost of the entire study. By equating the ratio between conditional power and initial power, the cost-benefit ratio is maintained. This means that the bar for conditional power for continuing gets progressively lower, as more of the total study costs become a “sunk cost.”

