**Efficacy Monitoring:** Although we neither recommend, nor anticipate, stopping early for efficacy, we recognize the need to provide for an exit strategy that permits a statistically valid conclusion to be drawn when it is desired to stop the trial and claim efficacy. We therefore propose using the efficacy stopping boundary proposed by Peto and Haybittle, namely we use a 2-sided nominal p-value of 0.001 for all interim looks (critical value 3.291), where the looks are at 40%, 60%, and 80% of information time, and we are thereby entitled to conduct the final test at the 0.0495 level (critical value = 1.965 rather than 1.960). This procedure accommodates the fact that our knowledge of information time is limited by the vagaries of incomplete (and changing) endpoint ascertainment and incomplete genetic ascertainment. The use of a fixed critical value independent of information time is very helpful in this unique context of uncertainty around the precise value of information time. This means a critical value of 3.291 would obtain at any interim look, independent of at what interim time the look occurred. At the final look, the critical value of 1.965 rather than 1.96 will be applied, which has an infinitesimal impact on power. We propose up to 3 interim looks, and that these occur at information times of approximately 40%, 60%, and 80%.

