where  $S(\cdot)$  is the overall underlying survival curve for freedom from events,  $t$  is time in years. Note that if the subject experiences the primary endpoint, the value of  $t$  is not tied to the event time itself, but rather reflects the visit date (roughly 1 month, 6 months, or one year) representing the effective amount of follow-up for that patient (time from randomization to last follow-up date). To calculate  $S(\cdot)$ , we simply use the Kaplan-Meier curve for the entire study population. This fraction therefore represents the fraction of a “risk year” to which that subject was exposed, i.e. it is an estimate of the proportion of events occurring within a year that have occurred at the follow-up time for the specific individual. Note that we consider  $w(t)$  to be a fixed quantity, rather than a parameter, though technically it is estimated from the entire data set.

We further assume that the event rates (1-year probabilities) are:

$$\lambda_{WT,CL} = \lambda_1$$

$$\lambda_{LOF,TIC} = \lambda_2$$

$$\lambda_{LOF,CL} = \lambda_3$$

We also assume that the rate of wild type subjects exposed to clopidogrel ( $\lambda_1$ ) is the same whether they are in the conventional therapy or the prospective genotyping group. This is a fundamental assumption, but one which will also be ultimately tested.

The treatment effect of interest can be expressed as  $\lambda_2/\lambda_3$ , that is, the relative risk associated with

ticagrelor in LOF subjects. The trial's primary hypothesis is that this number is substantially less than 1.0. (Relative risk reduction is 1 minus this quantity). Finally, let  $\alpha$  be the population prevalence of the LOF genotype in the population being randomized. We can now define the likelihood contributions of members of each of the three groups of "incomplete" subjects.

For those in the PG-WT and PG-LOF groups, the likelihood contributions, respectively, are:

$$L(\lambda_1|X, t) = [\lambda_1 * w(t)]^X * [1 - \lambda_1 * w(t)]^{(1-X)}$$

$$L(\lambda_2|X, t) = [\lambda_2 * w(t)]^X * [1 - \lambda_2 * w(t)]^{(1-X)}$$

For those in the CT group, the likelihood contribution is a weighted average of the likelihood contributions that would be obtained under (WT, CLOP) and (LOF, CLOP) conditions, weighted by the probability of each genotype, namely:

$$L(\lambda_1, \lambda_3, \alpha|X, t) = (1 - \alpha) * L_1(X, t) + \alpha * L_3(X, t)$$

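### Section 15.5 tests Hypothesis 1A at 0.05, but Section 15.8 sets the final test at 0.0495; separately, Appendix C leaves the sign of Z_t unstated

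*Combined protocol and SAP*

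**What the plan says.** **Final threshold.** Section 15.5 specifies a two-sided likelihood ratio test for Hypothesis 1A to "assess the significance of the partial effect of treatment; a p-value less than 0.05 will be considered statistically significant". It does not mention the interim looks or refer to Section 15.8.

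Section 15.8 (Efficacy Monitoring) allows up to three looks, at about 40%, 60% and 80% of information, each at a nominal two-sided 0.001 (critical value 3.291). The trial is "thereby entitled to conduct the final test at the 0.0495 level". The rule is then repeated without condition: "At the final look, the critical value of 1.965 rather than 1.96 will be applied".

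The formal test of Hypothesis 1B in Section 15.5 opens with "If the null hypothesis in 1A is rejected" and names no level for that rejection.

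**Sign of Z_t.** Section 15.8 introduces the monitoring statistic with "Once we have a current z-score (effect divided by standard error" and leaves the detail to Appendix C. There, "The treatment effect of interest can be expressed as" λ2/λ3, ticagrelor over clopidogrel in carriers, and the trial's "primary hypothesis is that this number is substantially less than 1.0". Z_t is to be obtained from the log of the estimated effect and its standard error. The result feeds the futility guideline, which asks that "consideration be given to stopping the trial if the ratio of conditional power to initial power falls below the proportion of remaining information time".

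**The concern.** A confirmatory test needs one success criterion, fixed in advance. Here a final p-value between 0.0495 and 0.05 is a success under the section that specifies the primary analysis and a failure under the section that specifies monitoring. The same p-value decides whether Hypothesis 1B is formally tested. Using 0.05 after spending alpha at the looks also puts the overall error slightly above the 0.05 stated in Section 2.1.

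The sign question is separate. The log of a ratio below 1 is negative, so a Z_t formed literally as log effect over standard error is negative under benefit. The conditional-power formula subtracts Z_t√t from +1.96 and credits a positive drift, so it needs Z_t positive under benefit. A programmer who followed the prose and not the worked figures would give the DSMB a conditional power that falls as the results improve.

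**Working it through.** **1. Final threshold**

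Inputs, all from Section 15.8: looks at t = 0.4, 0.6, 0.8; interim boundary |Z| > 3.291; final critical value c at t = 1. Under the null the Z-values are jointly normal with correlation √(s/t) for s < t. Overall alpha is the probability of crossing at any look, found by recursive numerical integration without a futility stop.

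First, the plan's own figure. Solving for overall alpha = 0.05 gives c = 1.9639, nominal p = 0.04955. The 0.0495 in Section 15.8 is therefore right to the precision shown.

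| Final rule | c | Overall two-sided alpha |
|---|---|---|
| p < 0.05 (Section 15.5) | 1.9600 | 0.05045 |
| p < 0.0495 (Section 15.8, level) | 1.9643 | 0.04995 |
| \|Z\| > 1.965 (Section 15.8, critical value) | 1.965 | 0.04987 |

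A simulation of 4 million paths agrees: 0.0504 for 1.960 and 0.0498 for 1.965. With only one look, at 40%, a final test at 1.960 gives 0.0504.

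Section 15.8 pairs 0.0495 with 1.965, but they are not quite the same threshold: 1.965 is p = 0.0494, and p = 0.0495 is 1.9643.

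Power: Appendix C gives 85.8%, so the expected final z is 1.960 + 1.071 = 3.031. At 1.9643 the power is Φ(3.031 − 1.964) = Φ(1.067) = 85.7%, a cost of about 0.1 point.

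Chance that the final p lies between 0.0495 and 0.05, ignoring early stopping:
- Null: 0.05 − 0.0495 = 0.0005, or 0.05%.
- HR 0.50: band width 0.0043 × normal density about 0.225 at distance 1.07 = 0.1%.
- HR 0.65 (mean z = 0.431/0.2287 = 1.88): 0.0043 × about 0.398 = 0.2%.

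**2. Sign of Z_t**

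First, the plan's own figures: |log 0.5|/3.031 = 0.6931/3.031 = 0.2287, and 1/0.2287² = 19.1. Both reproduce in absolute value. As printed, log(0.5)/3.031 is −0.2287.

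Formula used, with P0 = 0.858:

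CP = 1 − Φ[(1.960 − Z_t√t)/√(1−t) − 3.031√(1−t)]

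In the text copy used here the bracket closes before the drift term, which would give values that are not probabilities. That is taken as a PDF-reading effect, and the drift is read inside Φ.

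At t = 0.6 the futility threshold is 0.858 × 0.4 = 0.343. For an observed HR of 0.50, SE = 0.2287/√0.6 = 0.2952 and |Z| = 0.6931/0.2952 = 2.348.
- Benefit positive: (1.960 − 1.819)/0.6325 − 1.917 = −1.694, so CP = 0.955.
- Literal sign: (1.960 + 1.819)/0.6325 − 1.917 = 4.057, so CP = 0.00002.

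For an observed HR of 2.0 the two results swap. Limits at which the guideline flags the trial:

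| Information | Benefit positive: flag if HR above | Literal sign: flag if HR below |
|---|---|---|
| 40% | 0.91 | 1.10 |
| 60% | 0.83 | 1.21 |
| 80% | 0.77 | 1.30 |

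If the true HR is 0.50, the chance of a flag at 60% information is 4.3% with benefit positive and 99.9% with the literal sign. The information times are illustrative here, because Section 15.8 applies the futility guideline at DSMB reviews.

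**The case against.** **On the threshold.** Section 15.8 names 1.96 and replaces it, so a specific rule can be said to govern the general one in Section 15.5, leaving only a cross-reference missing. Section 15.8 also says that the effect on power is negligible, and Hypothesis 1B is meant to confirm a null. The point about size stands. The conflict remains, because neither section says which prevails and Section 15.5 is the one headed as specifying the primary analyses. If no efficacy look were taken, 0.05 would be valid, but Section 15.8 does not make 1.965 conditional on a look. A reader might infer that Section 2.1 conflicts too. It does not: its 0.05 is the overall rate, which Section 15.8 delivers. The 0.05 level for 1B itself is not in question.

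**On the sign.** A reader might go further and say that the plan defines Z_t with the wrong sign and that its futility rule is therefore reversed. The documents do not support that. Appendix C names the ingredients of Z_t and gives no equation. Its worked example maps a hazard ratio of 0.50 to an expected z of +3.031 with a standard error of +0.2287, so the intended direction is visible. A minus sign could also have been lost in the PDF reading. The near-zero conditional power at HR 0.50 is what a coding slip would produce, not an operating characteristic of the plan, and a statistician would probably notice it. The guideline is advisory, and the DSMB also receives an updated unconditional power and the carrier event rate with its interval. What stands is that the convention is nowhere stated. Taking absolute values would not be a safe substitute, because harm would then count as benefit.

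**Conclusion.** The threshold conflict is real and small. After looks at 40%, 60% and 80%, the Section 15.5 rule gives overall alpha of about 0.0505 against the stated 0.05, and the 0.0495 level gives 0.04995. This rests on the stated look times and boundary and on no credit for futility stopping. The reason to act is that the primary success criterion, and with it the gate to 1B, should have a single value.

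The sign of Z_t is a clarification. The intended convention can be read from the worked figures, but the literal wording points the other way and would reverse the futility guideline if coded as written. The efficacy boundary is two-sided and is unaffected. Overall severity: minor.

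**What to change.** 1. Section 15.5, Hypothesis 1A: *a two-sided p-value less than 0.0495 (see Section 15.8) will be considered statistically significant.*
2. Section 15.5, gate to 1B: make the condition rejection of the 1A null hypothesis at that level. Leave the 0.05 level for 1B unchanged.
3. Section 15.8: give the critical value for 0.0495 as 1.964 in place of 1.965, so that the level and the critical value are one threshold.
4. Appendix C, conditional power: use 1.964 as the success boundary in place of 1.96. The other Φ⁻¹(0.975), which with P0 forms the drift of 3.031, can stay, because the 85.8% power was calculated at 0.05. Even with 1.965 as the boundary, conditional power changes by less than 0.005.
5. Appendix C: state *Z_t = −log(λ2/λ3)/SE[log(λ2/λ3)], positive when ticagrelor has fewer events*, print the standard error as −log(0.5)/3.031, and refer to this convention where Section 15.8 introduces the z-score.

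These are wording edits. Sample size, number and timing of looks, the interim boundary, Section 2.1 and Section 15.2.2 need no change. The cost is the 0.1 point of power that Section 15.8 already accepts.
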